6.3 Exclusion Criteria

Patients will be excluded from the study if they meet **any** of the following criteria:

1. Treatment within the last 30 days with a drug that has not received regulatory approval for any indication at the time of study entry or used an investigational device within 4 weeks of the first dose of treatment.
2. Has a known history of active TB (*Bacillus Tuberculosis*).
3. Hypersensitivity to pembrolizumab or any of its excipients.
4. Concurrent administration of any other anti-tumor therapy.
5. Has received prior therapy with an anti-PD-1, anti-PD-L1, or anti-PD-L2 agent.
6. Has known active Hepatitis B (e.g., HBsAg reactive) or Hepatitis C (e.g., HCV RNA [qualitative]).
7. Inability to comply with protocol or study procedures.
8. Active infection requiring antibiotics, antifungal or antiviral agents, that in the opinion of the investigator would compromise the patient's ability to tolerate therapy.
9. Has known history of, or any evidence of active, non-infectious pneumonitis that required steroids (steroid treatment of COPD or asthma allowed).
10. Has a known history of Human Immunodeficiency Virus (HIV) (HIV 1/2 antibodies).
11. Has active autoimmune disease that has required systemic treatment in the past 2 years (i.e. with use of disease modifying agents, corticosteroids or immunosuppressive drugs). Replacement therapy (e.g. thyroxine, insulin or physiologic corticosteroid replacement therapy for adrenal or pituitary insufficiency etc.) is not considered a form of system treatment. Patients with a history of inflammatory bowel disease, including ulcerative colitis and Crohn's Disease, are excluded from this study, as are patients with a history of symptomatic disease (e.g., rheumatoid arthritis, systemic progressive sclerosis [scleroderma], systemic lupus erythematosus, autoimmune vasculitis [e.g., Wegener's Granulomatosis]); motor neuropathy considered of autoimmune origin (e.g. Guillain-Barre Syndrome and Myasthenia Gravis).
12. Has a diagnosis of immunodeficiency or is receiving systemic steroid therapy or any other form of immunosuppressive therapy within 7 days prior to the first dose of trial treatment.
13. Has a known additional invasive malignancy that is progressing or requires active treatment. Exceptions include basal cell carcinoma of the skin or squamous cell carcinoma of the skin that has undergone potentially curative therapy or in situ cervical cancer.
14. Is pregnant or breastfeeding, or expecting to conceive or father children within the projected duration of the trial, starting with the pre-screening or screening visit through 120 days after the last dose of trial treatment.
15. Has had major surgery (other than definitive lung cancer surgery) within two weeks of study or other serious concomitant disorders that in the opinion of the investigator would compromise the safety of the patient or compromise the patient's ability to complete the study.
16. Has received any non-oncology vaccine therapy used for prevention of infectious diseases (for up to 30 days before or after any dose of pembrolizumab). *Note: Seasonal influenza vaccines for injection are generally inactivated flu vaccines and are allowed; however, intranasal influenza vaccines (e.g., Flu-Mist®) are live attenuated vaccines and are not allowed.*

17. Has history of myocardial infarction having occurred less than 6 months before inclusion, any known uncontrolled arrhythmia, symptomatic angina pectoris, active ischemia, or cardiac failure not controlled by medications. Patients with CAD recently treated with surgery and/or stent, if stable without symptomatic angina pectoris, active ischemia are eligible.
18. Has evidence or a history of interstitial lung disease.
19. Has known psychiatric or substance abuse disorders that would interfere with cooperation with the requirements of the trial.
20. Prisoners or subjects who are compulsorily detained involuntarily incarcerated) for treatment of either psychiatric or physical (e.g., infectious) illness.

6.4 Protocol Eligibility Waivers

No waivers of inclusion or exclusion criteria will be granted. All prospective patients must meet all entry criteria prior to enrollment in the study. If there are any questions regarding the interpretation of a criterion for a potential patient, contact the principal investigator to discuss the potential patient to confirm eligibility.

7.0 INCLUSION of WOMEN and MINORITIES

There are no exclusions based on gender, race or ethnicity in this trial. There is no evidence to suggest that outcomes will differ.

8.0 REGISTRATION PROCEDURE

Patient registration for all patients signing informed consent will be completed through the Duke Cancer Institute (DCI) Clinical Research Unit (CRU) into eResearch (DOCR). The investigator and/or designee will enter the patient information into the DOCR Subject Registry within 1 business day of obtaining consent. Patients will be enrolled only after all pre-treatment evaluations are completed and all eligibility criteria are met. For patients enrolled at Duke Cancer Institute, patient information will also be entered into MaestroCare at the time of enrollment, linking the patient to the research subject record (RSH), to the study encounter and the timeline (if applicable) prior to the close of the study encounter.

8.1 Registration Procedure for Outside Sites

All patients signing informed consent at outside sites must be registered with Duke (including screen failures – indicate screen failure status on last page of eligibility checklist). Redacted enrollment packet will be completed by the investigator and/or designee and faxed to the Thoracic Oncology Protocol Office at [contact] at the time of registration. This includes:

- TOP 1501 Eligibility Checklist
- Signed informed consent

Patients will be enrolled only after all pre-treatment evaluations are completed and all eligibility criteria are met and confirmed by Duke.

9.0 STUDY PERIODS (Visit Requirements)

The Study Schedule (Appendix A) summarizes the trial procedures to be performed at each visit. Individual trial procedures are described in detail below. It may be necessary to perform these procedures at unscheduled time points if deemed clinically necessary by the investigator.

For the purpose of scheduling evaluations and to allow for patient and investigator schedules, holidays and weather or other emergencies requiring clinical facilities to be closed, all patient visits can be performed ± 3 days of scheduled visits.

Furthermore, additional evaluations/testing may be deemed necessary by the Sponsor and/or Merck for reasons related to subject safety. In some cases, such evaluation/testing may be potentially sensitive in nature (e.g., HIV, Hepatitis C, etc.), and local regulations may require that additional informed consent be obtained from the subject. In these cases, such evaluations/testing will be performed in accordance with those regulations.

9.1 Screening

The following procedures and tests are to be performed within **30** days (unless otherwise specified) of study enrollment to confirm eligibility. Baseline and Cycle 1 Day 1 procedures may be completed on the same day. However, screening assessments for *eligibility* **MUST** have already been determined. Refer to Appendix A for details. Refer to Table 5 for specific laboratory test information.

- Informed Consent
- Eligibility
- Medical history including demographics/smoking history
- Height and weight (BSA calculation)
- Vital signs (temp, B/P, pulse)
- ECOG Performance status
- Physical exam
- Routine blood work (CBC, Chemistries)
- Calculated creatinine clearance
- Thyroid Functions (T3, FT4 & TSH)
- Coagulation (aPTT, PT(INR))
- Routine Urinalysis
- Negative Pregnancy test for WOCBP only
- EKG

- Tumor Histology
- Medical and Surgical Evaluation
- Staging PET/CT of chest/abdomen, Brain MRI or CT (as per standard of care) These may be obtained within 42 days
- Tumor measurement to ensure primary lesion ≥ 3 cm
- PFTs (FEV1 and DLCO)
- Research blood (1st Collection): blood will be collected to assess longitudinal analyses of T cell and MDSC phenotypes and blood based biomarkers. 4 tubes of 8.5-ml each will be collected. The tubes used will be ACD anti-coagulated Vacutainer (yellow tops). Samples will be collected prior to pembrolizumab initiation (may be collected Day 1 cycle 1 pre-infusion), and transported/shipped to the Substrate Services Core lab for processing. (Refer to Appendices F and G)

9.2 Neoadjuvant Pembrolizumab Treatment (Cycle 1, Day 1)
(To be performed prior to receiving treatment-refer to Appendix A)

- Weight (BSA calculation)
- Vital signs (temp, B/P, pulse)
- ECOG Performance status
- Physical exam
- Adverse events assessment
- Routine blood work
- Pregnancy test ≤ 3 days (72 hrs.) prior to first dose of pembrolizumab (for WOCBP only)
- Dose # 1 Pembrolizumab 200 mg IV

9.3 Neoadjuvant Pembrolizumab Treatment (Cycle 2, Day 22)

- Weight (BSA calculation)
- Vital signs (temp, B/P, pulse)
- ECOG Performance Status
- Physical exam
- Adverse events assessment
- Routine blood work
- Dose #2 Pembrolizumab

9.4 Evaluation at Completion of Neoadjuvant Pembrolizumab and Prior to Surgery.

Final visit (if ≤ 1 grade 1 toxicity) for those subjects that come off treatment early for progression of disease, intolerance to protocol therapy, other reasons, or patient withdraws consent. Safety

Evaluation should occur 30 days (+/- 5 days) after last dose of pembrolizumab or before initiation of a new anti-neoplastic cancer treatment (whichever comes first).

- Medical and Surgical evaluation after completion of pembrolizumab
- Weight
- Vital signs (temp, B/P, pulse)
- ECOG Performance status
- Physical Exam
- Routine Blood work
- Thyroid Functions (T3, FT4, & TSH)
- Repeat imaging to evaluate tumor (Chest CT)
- Adverse events assessment
- Research blood (2nd Collection): blood will be collected to assess longitudinal analyses of T cell and MDSC phenotypes and blood based biomarkers. 4 tubes of 8.5-ml each will be collected. The tubes used will be ACD anti-coagulated Vacutainer (yellow tops). Samples will be collected, and transported/shipped to the Substrate Services Core lab for processing. (Refer to Appendices F & G)

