11. Females of child-bearing potential (not surgically sterilized or postmenopausal [a woman who is ≥ 45 years of age and has not had menses for greater than 1 year]) must test negative for pregnancy within 48 hours prior to any initial study procedure based on a serum pregnancy test. Both sexually active males and females of reproductive potential must agree to use a reliable method of birth control, as determined by the patient and their health care team, during the study and for 120 days following the last dose of study drug. If subject uses appropriate contraceptive methods (the use of two forms at the same time) from the time of the initial serum pregnancy test, then the subsequent pregnancy test can be done within 72 hours of receiving study drug administration. If appropriate; contraceptive measures are not begun immediately with the first serum pregnancy test, then subsequent serum pregnancy tests must be done within 48 hours prior to the study drug administration.
12. Patients must agree to research blood sampling to participate in study.
13. Have measurable disease based on RECIST 1.1.
14. FEV1 and DLCO $\geq 40\%$ predicted (or per institutional standard).

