14.3 Use in Pregnancy

If a subject inadvertently becomes pregnant while on treatment with pembrolizumab, the subject will immediately be removed from the study. The site will contact the subject at least monthly and document the subject's status until the pregnancy has been completed or terminated. The outcome of the pregnancy will be reported to the Sponsor and to Merck without delay and within 24 hours to the Sponsor and within 2 working days to Merck if the outcome is a serious adverse experience (e.g., death, abortion, congenital anomaly, or other disabling or life-threatening complication to the mother or newborn).

The study investigator will make every effort to obtain permission to follow the outcome of the pregnancy and report the condition of the fetus or newborn to the Sponsor. If a male subject impregnates his female partner the study personnel at the site must be informed immediately and the pregnancy reported to the Sponsor and to Merck and followed as described above and in Section 20.4.

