15.1 Subject Withdrawal/Discontinuation Criteria

The End of Treatment and Follow-up visit procedures are listed in Appendix A (Study Schedule) and Section 9.0 (Study Periods-Visit Requirements). After the end of treatment, each subject will be followed for 30 days for adverse event monitoring (serious adverse events will be collected for 90 days after the end of treatment (Section 20.5.1). Subjects who discontinue for reasons other than progressive disease will have post-treatment follow-up for disease status until disease progression, initiating a non-study cancer treatment, withdrawing consent or becoming lost to follow-up. For all other subject's outcome data will be collected for 2 years, then every 6 months for up to five years. Every effort should be made to collect information regarding disease during this follow-up which may include the start of new anti-neoplastic therapy, disease progression, death, or end of study. When a subject discontinues/withdraws prior to trial completion, all applicable activities scheduled for the final trial visit should be performed at the time of discontinuation. Any adverse events which are present at the time of discontinuation/withdrawal should be followed in accordance with the safety requirements outlined in Section 9.8.5& 20. .

A subject must be discontinued from the trial for any of the following reasons:

- The subject or legal representative (such as a parent or legal guardian) withdraws consent.

- Confirmed radiographic disease progression

Note: For unconfirmed radiographic disease progression, please see Section 17.3.1. A subject with evidence of possible target lesion growth or new lesion appearance will not be presumed to have progressed and will proceed to surgery as long as all possible site(s) of disease are deemed resectable by the surgeon.

- There is toxicity deemed by the investigator or subject to be unacceptable
- Concurrent illness that prevents further administration of treatment
- Investigator's decision to withdraw the subject
- The subject has a confirmed positive serum pregnancy test
- Noncompliance with trial treatment or procedure requirements
- The subject is lost to follow-up
- Administrative reasons
- The investigator, for any reason, stops the study
- Termination of the study by Merck

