29.1 Appendix A: STUDY SCHEDULE

Examination	Baseline (screen) ^a	Neoadjuvant RX		Evaluation post pembro ^k	Surgery ^p	Post Surgery FU ^r
		Cycle1	Cycle 2			
Day	30 to 0	1 (+/- 3 days)	22 (+/- 3 days)	pre-surgery	29 – 56 (from C1D1)	2-6 wks. post Surgery
Informed Consent	X					
Eligibility	X					
Medical Hx/Demo/ Smoking Hx	X					
Height	X					
Vital Signs (temp, RR, B/P, pulse)	X	X	X	X		X
Weight/BSA	X	X	X	X		X
Physical Exam	X	X	X	X		X
Performance Status	X	X	X	X		X
Hematology ^{b,c,e}	X	X	X	X		X
Chemistries ^{b,d,e}	X	X	X	X		X
Serum Beta HCG ^h	X	X ^h				
Calculated Creatinine ^{e,f} Clearance	X					
Thyroid Functions (T3, FT4, TSH) ^e	X			X		
PT(INR), aPTT ^e	X					
Urinalysis	X					
PFTs (FEV1/DLCO) ^e	X					
Radiologic Eval ^g	X			X ^g		X ^g
Medical & Surgical Evaluation	X			X		
EKG	X					
Tumor Histology	X					
Adverse Events		X	X	X		X
Concomitant Meds	X	X	X	X		X

Pembrolizumab		X	X			
Blood Sampling ^j	X ^j			X ^j		X ^j
Surgical Specimen ^p					X	
Tumor Biopsy Slides ⁿ					X	
Examination	STD ADJ CT/RT ^l	Adjuvant Pembrolizumab ^m				EOS ^s Follow-Up
		Cycle 1 ^m	Cycle 2	Cycle 3	Cycle 4	
Day		1	22	43	64	≥30 d post Pembro ^j
Informed Consent						
Eligibility						
Medical History/Demo- Graphics/Smoking Hx						
Height						
Vital Signs (temp, RR, B/P, pulse)		X	X	X	X	X
Weight/BSA		X	X	X	X	X
Physical Exam		X	X	X	X	X
Performance Status		X	X	X	X	X
Hematology ^{b,c,e}		X	X	X	X	X
Chemistries ^{b,d,e}		X	X	X	X	X
Serum Beta HCG ^h		X	X	X	X	
Thyroid Functions (T3, FT4, TSH) ^e		X		X		X
PT(INR), aPTT ^e						
Urinalysis						
PFTs (FEV1/DLCO) ^e						
Radiologic Evaluation ^g						
Med/surg Evaluation						
EKG						

Tumor Histology						
Adverse Events		X	X	X	X	X
Concomitant Meds		X	X	X	X	X
Pembrolizumab		X	X	X	X	
Blood Sampling ^j						X ^j
Surgical Specimen ^p						
Tumor Biopsy Slides ⁿ						

To allow for patient and investigator schedules, holidays, weather or other emergencies requiring facilities to be closed, visits can be performed ±3 days of scheduled visit

a Pre-enrollment baseline (screen) assessments are to be performed within -30 to 0 days unless otherwise specified.

b May be obtained within 3 days of pembrolizumab dosing

c Hematology values to include Hgb/Hct, WBC with auto or manual differential, platelets

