d Chemistries to include Na⁺, K⁺, Cl⁻, total protein, albumin, calcium, glucose, BUN, creatinine, total bilirubin (direct bilirubin if total is elevated above upper limit of normal), alkaline phosphatase, SGOT, SGPT, LDH, uric acid, magnesium, phosphorus. **e** Baseline required labs to be performed within 30 days of enrollment Pre-study tests may be used for day 1, cycle 1 tests if obtained within 14 days of day 1 cycle 1 treatment. PFT's per institutional standards.

f Calculated creatinine clearance (see appendix D)

g Radiologic evaluation: pre-treatment clinical staging PET/CT of chest/abdomen, brain MRI or CT as per standard of care (these may be performed up to 42 days); after completing cycle#2 Pembrolizumab therapy (prior to surgery) chest CT; post- surgery recommend chest CT every 3-4 months (or per institutional standard of care) for 2 years

h All WOCBP MUST test negative for pregnancy within 48 hours prior to any initial study procedure based on a serum pregnancy test. If subject uses appropriate contraceptive methods (section 6.2) from the time of the initial serum pregnancy test, then the subsequent pregnancy test can be done within 72 hours before receiving pembrolizumab. If appropriate contraceptive methods are not begun immediately with the first serum pregnancy test, then subsequent serum pregnancy tests must be done within 48 hours prior to the study drug administration. If the pregnancy test is positive, the subject must not receive pembrolizumab and must not be enrolled in the study, or will be removed from treatment.

j Blood samples to assess activated CD8+ T cells with specificity against tumor antigens and CD4 and CD8 functional memory. **Collection 1:** Baseline: pre-dose #1 pembrolizumab. **Collection 2:** After second dose of Pembrolizumab (cycle 2) and prior to surgery. **Collection 3:** 2-6 weeks after surgery. **Collection #4:** Three to 6 weeks after last dose of adjuvant pembrolizumab. 4 tubes of 8.5 ml each (ACD anti-coagulated Vacutainer yellow tops).

k Evaluation Post pembrolizumab prior to surgery. Final visit (if \leq grade 1 toxicity) for those subjects that come off treatment early for progression of disease, intolerance to protocol therapy, for other reasons, or patient withdraws consent; safety evaluation should occur 30 days (+/- 5days) after last dose pembrolizumab or before initiation of a new anti-neoplastic cancer treatment (whichever comes first).

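### Neoadjuvant dose 2 (day 22) is the only one of six pembrolizumab doses with no scheduled pregnancy test; a minor gap in the safety schedule

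*Combined protocol and SAP*

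**What the plan says.** Section 9.3 gives seven items for day 22: weight, vital signs, performance status, physical exam, adverse events, routine blood work and "Dose #2 Pembrolizumab". No pregnancy test is among them. In Appendix A the "Serum Beta HCG" row is marked at baseline, at neoadjuvant cycle 1 and at all four adjuvant cycles, and is blank at neoadjuvant cycle 2.

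Inclusion criterion 11 (section 6.2) sets the timing of later tests, and Appendix A note h repeats it. For a woman using two contraceptive methods from the initial test, "then the subsequent pregnancy test can be done within 72 hours of receiving study drug administration". If contraception was not begun with that first test, "subsequent serum pregnancy tests must be done within 48 hours prior to the study drug administration".

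Three places deal with a pregnancy once it is known. Under note h, after a positive test "the subject must not receive pembrolizumab and must not be enrolled in the study, or will be removed from treatment". Section 14.3 states: "If a subject inadvertently becomes pregnant while on treatment with pembrolizumab, the subject will immediately be removed from the study". Section 15.1 lists among its reasons for discontinuation: "The subject has a confirmed positive serum pregnancy test".

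**The concern.** Section 14.2 warns that pembrolizumab may harm a fetus, and the three removal rules work only after a pregnancy has been found. At five doses a scheduled test does the finding. At dose 2 it depends on the patient noticing, or on the investigator ordering an unscheduled test, which section 9.0 allows. A woman who conceived around or after dose 1 could receive dose 2 with the schedule followed exactly. The pre-surgery evaluation in section 9.4 has no test either, so the next scheduled one is at adjuvant cycle 1, months later.

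The stake is one avoidable extra exposure in a small subgroup. The primary endpoint, the sample size and the analyses are untouched.

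**Working it through.** **Step 1. Compare the visit lists with the Appendix A row.**

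| Dose | Visit list | Test in list | Test in Appendix A |
|---|---|---|---|
| Neoadjuvant 1 | 9.2 | yes | yes |
| Neoadjuvant 2 | 9.3 | **no** | **no** |
| Adjuvant 1 | 9.8.1 | yes | yes |
| Adjuvant 2 | 9.8.2 | yes | yes |
| Adjuvant 3 | 9.8.3 | yes | yes |
| Adjuvant 4 | 9.8.4 | yes | yes |

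Doses with a scheduled test: 1 + 4 = 5 of 6. All six are 200 mg, given 21 days apart within each phase. Two separate places agree on the blank, so it is not a fault of table extraction.

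**Step 2. Age of the last scheduled test at dose 2.** The plan states no figure to reproduce. The inputs are:

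- interval from dose 1 to dose 2: 21 days (11.1);
- lead time from test to dose 1: 0–3 days under the 72-hour rule (9.2), or 0–2 days under the 48-hour rule (6.2 item 11, note h);
- administrative window: ±3 days (11.3.2);
- longest delay: 14 days for a related adverse event (11.4); 21 days under 11.1 and 15.1.

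Age = 21 + delay + window shift + lead time, counted from the actual date of dose 1.

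| Timing of dose 2 | Study day | Age, 72-hour rule | Age, 48-hour rule |
|---|---|---|---|
| On schedule | 22 | 21 to 21+3 = 21–24 | 21–23 |
| On schedule, ±3 days | 19–25 | 21−3 to 21+3+3 = 18–27 | 18–26 |
| 14-day delay | 36 | 35 to 35+3 = 35–38 | 35–37 |
| 21-day delay | 43 | 42 to 42+3 = 42–45 | 42–44 |

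The window is not added to the delayed rows, because 11.1, 11.4 and 15.1 already cap the delay. A delayed dose 2 is foreseen in section 9.5. Dose 2 on day 43 can still come before surgery: 43 + 2 = day 45, inside the day 29–56 window.

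With a test added at day 22, the age would be 0–3 days (0–2 under the 48-hour rule), with or without a delay.

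**Step 3. Does the wording require a test that the schedule omits?** The 48-hour sentence speaks of tests in the plural, tied to giving the drug. For women it covers, it can be read to require a test before dose 2, and neither 9.3 nor Appendix A carries one. The 72-hour sentence speaks of one later test, which the test before dose 1 can satisfy.

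**Step 4. Number of women.** The document does not give the number of women of childbearing potential. As an assumption without support in the document, take 0% to 10% of 30–35 patients: 0% × 30 = 0 to 10% × 35 = 3.5.

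**The case against.** The strongest reply is that the protocol already does nearly enough. A negative serum test is needed before any initial study procedure, and another before dose 1. Patients who are pregnant or expecting to conceive are excluded. Section 14.2 requires two contraceptive methods from Visit 1 and bars anyone whose compliance is in doubt. That nearly empties the 48-hour branch, the only one in which the wording and the schedule may pull apart. Any woman left in it may already be covered by the plural wording. All of this stands. It limits the size of the point, but it does not put a test on the day-22 schedule that sites follow.

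The comparison with the adjuvant doses is also softer than a bare count of 5 against 1 suggests, because the adjuvant lines are qualified by institutional guidelines. A reader might go further and infer that adjuvant cycles 2–4 lose their tests too, since those lines refer to the first dose. The document does not support that: Appendix A marks a test at each adjuvant cycle.

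Timing counts against urgency. The page footer is dated 11 November 2018, and the trial summary in section 3.1 gives about three years of enrolment from the third quarter of 2016. Roughly 26–28 of 36 months would have passed. Assuming even accrual, 8/36 × 32 ≈ 7 to 10/36 × 35 ≈ 10 patients would remain; at 0–10% that is 0 to 1 woman. Actual accrual is not documented, so this supports a low priority rather than dismissal.

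Finally, a day-22 test cannot undo exposure from dose 1: section 2.4 reports target engagement beyond 21 days. It can prevent only the exposure that dose 2 adds.

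**Conclusion.** The point holds as a minor schedule correction. Dose 2 is the only one of six doses without a scheduled test, and the last scheduled test is 18–27 days old at an on-schedule dose, 35–38 days after a 14-day delay and 42–45 days after a 21-day delay. These figures rest on counting from the actual date of dose 1 and on treating the delay limits as limits.

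Three stronger readings are tempting, and the document does not support them.

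- A reader might infer that the plan allows dosing in a known pregnancy. It does not: note h, 14.3 and 15.1 all require removal.
- A reader might infer a conflict with the eligibility rule for every woman of childbearing potential. For those on two methods there is none, only an unexplained difference from the adjuvant schedule. For the others, the plural wording can be read to require the test, which is as far as the text goes.
- A reader might add the ±3-day window to the delays and quote 32–48 days. Its lower end is an 11-day delay (day 33), and its upper end a 24-day delay (day 46), beyond the 21-day limit. A delay of 14 to 21 days gives 35–45 days.

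The number of women affected is probably very small and may be zero.

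**What to change.** For women of childbearing potential:

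- In 9.3, add a line: *serum beta-hCG before dose 2, within the 72 h or 48 h window of Appendix A note h*.
- In Appendix A, enter an X with note h at neoadjuvant cycle 2 in the "Serum Beta HCG" row.
- In 9.8.2–9.8.4, reword the pregnancy-test line so that it refers to that cycle's dose rather than the first dose, leaving the reference to institutional guidelines as it is.

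The routine blood draw already listed at day 22 can supply the sample. Note b says of that blood work: "May be obtained within 3 days of pembrolizumab dosing". That fits the 72-hour rule. Women under the 48-hour rule need the draw timed to 48 hours, or a separate one.

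The cost is one extra assay for a few women, possibly none, and a possible retimed draw. No endpoint or analysis changes. Because section 22.3 requires Duke IRB approval and sends amendments to the sites for local approval, the change should travel with the next amendment rather than prompt one.
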